3.1.2 Study duration

The study starts with the first act of recruitment (i.e., signed ICF) and ends with the last EOS visit of the last subject. The duration of the study is expected to be approximately 9–12 months.

End-of-Study for a single subject is defined as the date of the EOS telephone call (Visit 4). If a subject withdraws consent, EOS is the date of consent withdrawal for this subject. If a subject is declared lost to follow-up [see also Section 8.2], EOS is the date of last successful contact for this subject.

Confidential

For an individual subject, the study is completed with the EOS telephone call. The duration of the study for an individual subject will be up to 68 days (including a 36-h treatment period with i.v. selexipag).

3.2 Study design rationale

This study has been designed to address the question whether subjects with PAH on oral selexipag can be safely switched to i.v. selexipag and vice-versa. The single-sequence 3-period cross-over design has been chosen to mimic the intended clinical use of i.v. selexipag. The study plans to enroll approximately 20 subjects and will aim for at least 10 subjects to be treated with an i.v. selexipag dose corresponding to the oral dose of 1200–1600 µg b.i.d.

Subjects with a minimum of 28 days stable (i.e., dose unchanged) Uptravi dose will be enrolled. Subjects will be hospitalized and switched from the Uptravi oral dose to the corresponding b.i.d. i.v. dose of selexipag for a treatment period of 36 hours (3 doses) which allows the steady state of selexipag to be reached again and is therefore considered sufficient to assess tolerability and evaluate PK.

3.3 Study committees

No committees will be involved in the design or conduct of the study.

4 SUBJECT POPULATION

4.1 Subject population description

This study will enroll male and female subjects diagnosed with Group 1 PAH [Galiè 2016], aged 18 to 75 years, who have been prescribed Uptravi (oral selexipag) as part of their standard treatment for PAH. Eligible subjects will be at a stable dose of Uptravi for at least 28 days prior to enrollment.

Subjects will be in WHO Functional Class (FC) I, II or III. They may be treated concurrently with a stable dose of diuretics or other PAH-specific medications which are not agonists of the IP receptor (i.e., ERA, PDE-5 inhibitors or sGC stimulators).

4.2 Rationale for the selection of the study population

The study population includes patients with PAH who have been prescribed Uptravi in compliance with local prescribing information (i.e., [Uptravi® SmPC](#) or [Uptravi® USPI](#)) as part of their standard treatment for PAH.

Stability of PAH-specific concomitant medications is an important pre-requisite to assess the safety and tolerability of the switch from Uptravi to i.v. selexipag. Therefore, patients who have been prescribed Uptravi and are currently treated at a stable dose are considered to represent an adequate study population to evaluate whether switching from

an oral dose of selexipag to a corresponding selexipag i.v. dose is well tolerated in subjects with stable PAH.

Subjects under 18 years are excluded due to absence of clinical experience and approval of selexipag for the treatment of pediatric patients. Subjects with significant cardiovascular, hepatic, or renal medical conditions are excluded since they could potentially be at greater risk of complications due to these pre-existing comorbidities, which could interfere with evaluation of study assessments and interpretation of study results.

4.3 Inclusion criteria

For inclusion in the study, all of the following inclusion criteria must be fulfilled. It is not permitted to waive any criterion:

1. Signed ICF prior to any study-mandated procedure.
2. Male and female subjects at least 18 to 75 years inclusive.
3. Subjects with PAH belonging to the Updated Clinical Classification Group 1 [Galiè 2016]
4. Subjects who have been prescribed Uptravi in compliance with local prescribing information (i.e., SmPC or USPI).
5. Stable PAH defined as WHO FC I–III at Visit 1 and Visit 2 and no change (i.e., introduction or dose change) in PAH-specific medication (i.e., ERA, PDE-5 inhibitor or sGC stimulator) and diuretics in the last 28 days prior to Visit 2.
6. Subjects currently treated with Uptravi at a stable dose (i.e., unchanged dose) for at least 28 days before Visit 2.
7. A woman of childbearing potential is eligible only if she has a negative urine pregnancy test at Visit 1 and at Visit 2.

4.4 Exclusion criteria

Subjects must not fulfill any of the following exclusion criteria. It is not permitted to waive any criterion:

1. Pregnant, planning to become pregnant or lactating.
2. Known and documented moderate or severe hepatic impairment.
3. Subjects having received gemfibrozil at any time since initiation of Uptravi.
4. Treatment with any prostacyclin and prostacyclin analogs within 28 days prior to Visit 1.
5. SBP < 90 mmHg at Visit 1 or at Visit 2.
6. Known or suspected uncontrolled hyperthyroidism.
7. Severe renal failure and ongoing or planned dialysis.

8. Any known factor or disease that might interfere with treatment compliance, study conduct, or interpretation of the results, such as drug or alcohol dependence or psychiatric disease.
9. Known concomitant life-threatening disease with a life expectancy < 12 months.
10. Treatment with another investigational treatment within 3 months of Visit 1.

4.5 Criteria for women of childbearing potential

4.5.1 Definition of childbearing potential

A woman is considered to be of childbearing potential unless she meets at least one of the following criteria:

- Previous bilateral salpingectomy, bilateral salpingo-oophorectomy or hysterectomy,
- Postmenopausal (defined as 12 consecutive months with no menses without an alternative medical cause [ICH M3 definition]),
- Premature ovarian failure (confirmed by a specialist), XY genotype, Turner syndrome, uterine agenesis.

The reason for not being of childbearing potential will be recorded in the Case Report Form (CRF).

4.5.2 Acceptable methods of contraception

Women of childbearing potential [see definition in Section 4.5.1] must continue following their local Uptravi® instructions (as indicated in USPI or SmPC, as applicable) with regard to use of methods of birth control from Screening (Visit 1) up to Visit 4.

The methods of birth control used (including non-pharmacological methods) must be recorded in the CRF.

5 TREATMENTS

5.1 Study treatment

5.1.1 Investigational treatment: description and rationale

Selexipag for i.v. administration will be supplied as 10 mL vials containing 1800 µg of dry powder of selexipag for injectable solution reconstitution.

The study treatment, i.v. selexipag, will be administered intravenously b.i.d. as an infusion over an 87-minute period [see Section 5.1.4]. The dose will be individualized for each subject and will correspond to subject's current dose of orally administered Uptravi.

Since selexipag's active metabolite ACT-333679 is up to 37-fold more potent than selexipag as an agonist of the human IP receptor in vitro, the i.v. formulation was

developed with the aim of reaching an exposure equivalent to the active metabolite (AUC between two doses) comparable to the one obtained with the oral formulation.

The correspondence between doses of Uptravi and i.v. selexipag doses were determined based on the results of the absolute bioavailability study (AC-065-110). The i.v. selexipag doses corresponding to the oral Uptravi doses are provided in [Table 1](#).

Table 1 Correspondence of i.v. selexipag doses to Uptravi oral doses

Uptravi oral dose (μ g)	Corresponding i.v. selexipag dose (μ g)
200	225
400	450
600	675
800	900
1000	1125
1200	1350
1400	1575
1600	1800

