1.2.4 Summary of clinical data

A comprehensive package of clinical studies was performed that supported the approval of selexipag as oral treatment for PAH. Details of the clinical development of selexipag oral formulation are described in the IB [\[Selexipag IB, Selexipag IB Amendment 1\]](#).

So far a different formulation of i.v. selexipag has been administered to 18 healthy male subjects in an absolute bioavailability study (AC-065-110) and has not been administered to subjects with PAH.

In the study AC-065-110, the geometric mean (95% confidence interval [CI]) of the area under the plasma concentration versus time curve (AUC) from 0 to infinity ($AUC_{0-\infty}$) of selexipag and ACT-333679 were 11.16 h·ng/mL (9.30, 13.38) and 14.91 h·ng/mL (11.42,

19.47), respectively, following a single i.v. infusion of 200 µg selexipag in healthy subjects. In the same study, following a single oral dose of 400 µg selexipag, geometric mean (95% CI) $AUC_{0-\infty}$ values of selexipag and ACT-333679 were 11.04 h·ng/mL (8.19, 14.87) and 37.97 h·ng/mL (30.18, 47.78), respectively. The exposure ($AUC_{0-\infty}$) to ACT-333679 was 1.34- and 3.44-fold higher than to selexipag after i.v. administration and oral administration, respectively. This difference in metabolite exposure is likely due to the first pass metabolism of oral selexipag [Selexipag IB, Selexipag IB Amendment 1].

Single doses of i.v. and oral selexipag were both well tolerated. The most frequently reported treatment-emergent adverse event (AE) was headache. All treatment-emergent AEs were of mild to moderate intensity. There were no serious adverse events (SAEs) and no AEs leading to discontinuation. No clinically significant treatment-emergent abnormality in clinical laboratory, vital signs, or ECG variables was observed.

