1.4 Summary of known and potential risks and benefits

There is no direct individual benefit for the subject to participate in the study.

Uptravi local prescribing information essentially constitutes the benefit-risk summary for selexipag [Uptravi® USPI, Uptravi® SmPC]. The short and long-term safety profile of oral selexipag (Uptravi) has been established in the GRIPHON study and is mainly characterized by inter-individual susceptibility towards prostacyclin-associated AEs

associated with the mode of action of selexipag. Such AEs typically occur during the phase of individualized dose titration. No new safety findings were observed after single administration of i.v. selexipag in healthy subjects. Hence, the safety profile of i.v. selexipag is expected to be identical to that of Uptravi. Moreover, the dose of i.v. selexipag that will be administered during the study will target the same exposure to selexipag's active metabolite ACT-333679 as with their prescribed dose of Uptravi. Hence, the risks associated to study participation are expected to be limited to the ones associated with any i.v. administration of drugs and with the invasive study-specific procedures (i.e., repeated blood sampling for pharmacokinetic [PK] and safety assessments).

The following measures are taken to minimize the risks for the subjects participating in the study:

- Exclusion of subjects with unstable PAH condition or severe co-morbidities [see Section 4.4].
- In-patient hospitalization during pre-treatment and treatment periods (Period 1 and 2).
- Close monitoring of the subjects throughout the study, including frequent monitoring of vital signs following initiation of i.v. selexipag infusion.

It is the investigator's responsibility to monitor the risk-benefit ratio of the study treatment administration, as well as the degree of distress caused by the study procedures on an individual subject level, and to discontinue the study treatment or the study if, on balance, he/she believes that continuation would be detrimental to the subjects' well-being.

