10.3.5 Analysis of PK variables

For all PK analyses, the Pharmacokinetic Analysis Set will be employed.

- Plasma concentrations of selexipag and ACT-333679 will be summarized per time point by dose and period using arithmetic mean, geometric mean, minimum, median,

maximum, standard deviation (SD), standard error (SE), and two-sided 95% CI of the means.

- $C_{trough, ss}$ of selexipag and ACT-333679 will be listed by dose, period and subject, and will be summarized by dose and period using arithmetic mean, geometric mean, minimum, median, maximum, SD, SE, and coefficients of variation (CV, CV_{ln}) in %, and two-sided 95% CI of the means.
- $C_{max, ss}$, $t_{max, ss}$, and $AUC_{\tau, ss}$ of selexipag and ACT-333679 will be listed by dose, period, and subject.
- $C_{max, ss}$, $t_{max, ss}^*$ and $AUC_{\tau, ss}$, will be summarized by dose and period with arithmetic mean, geometric mean, minimum, median, maximum, SD, SE, $CV\%$ and $CV_{ln}\%$, 95% CI of the arithmetic and geometric means, and inter-subject coefficient of variation (CV_b). (* For $t_{max, ss}$, the geometric mean, its 95% CI and CV_{ln} will not be calculated).
- Differences in $C_{max, ss}$ and $AUC_{\tau, ss}$ of selexipag and ACT-333679 between periods will be explored after dose normalization and within each dose level by using the 90% CI of the ratio of the geometric means of selexipag i.v. (test treatment) versus selexipag oral (reference treatment). The log-transformed values will be analyzed by mixed-effect models including treatment and period as fixed effects and subject as random effect. The ratios of geometric means and their 90% CI will be calculated from the corresponding back log-transformed contrasts of the mixed-effects models for $C_{max, ss}$ and $AUC_{\tau, ss}$ of selexipag and ACT-333679 after oral or i.v. selexipag administration.
- Differences for $t_{max, ss}$ of ACT-333679 between periods will be explored within each dose level using the Wilcoxon signed rank test providing the median differences and their 90% CI.
- Dose proportionality for $AUC_{\tau, ss}$ of selexipag and ACT-333679 after selexipag i.v. will be explored by the power model as described by [Gough 1995], (this analysis will only be done if there are at least 3 different doses in the study).
- $C_{max, ss}$ and $AUC_{\tau, ss}$ ratio of ACT-333679 / selexipag will be listed by dose, period, and subject and will be summarized by dose and period.

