4.1.5 Pharmacokinetic Analysis Set

The Pharmacokinetic Analysis Set (PKS) comprises all subjects included in the SAF who received an Uptravi dose on Day 1 and the three doses of i.v. selexipag, and who complied with the protocol in a way that the PK measurements of the study are not affected. Protocol deviations resulting in an exclusion from the PKS are shown in [Table 3](#).

Additional rules for exclusion from the PKS may be defined prior to database lock and reflected in this document.

Table 3 Protocol deviations leading to an exclusion from the PKS

Category	Protocol deviation code(s)	Identifier	Level of exclusion
Protocol deviation during screening period	206	Dose of Uptravi not stable for at least 28 days before Visit 2 (INCL 6)	Subject
	209	Subject with known and documented moderate and severe hepatic impairment (EXCL 2)	Subject
	210	Subject received gemfibrozil at any time since initiation of Uptravi (EXCL 3)	Subject
	214	Subject with renal failure and ongoing or planned dialysis (EXCL 7)	Subject
	217	Subject with another investigational treatment within 3 months of Visit 1 (EXCL 10)	Subject
Protocol deviation during treatment and observation period	305	Pre-dose PK blood sample collected after the morning dose on Day 1 or Day 3	Data point*
	306	Any post-AM dose PK sample collected after administration of the following PM dose on Day 1 or Day 3	Data point*
	316	Uptravi was not interrupted during i.v. selexipag treatment	Subject
	312	25 min or 87 min post-infusion start PK blood sample on Day 3 collected from the same arm as the infusion line	Data point*
	313	Subject did not discontinue i.v. selexipag treatment despite missing one infusion	Subject
	318	Dose of PAH medications (including diuretics) not stable between Visit 1 (screening) and last PK blood sample collection on Day 3	Subject
	321	Uptravi not administered or Uptravi dose missing on Day 1	Subject
	322	Uptravi dose on Day 1 is different from stable dose at Visit 1 (screening)	Subject
	323	Any i.v selexipag dose is not corresponding to subject's stable dose of Uptravi (i.e., ≥ 225 ug)	Subject

* If 2 or more data points are excluded from a 12-hour PK profile (i.e., on Day 1 or Day 3), the subjects must be excluded from the PKS. i.v. = intravenous; PK = pharmacokinetic; PKS = Pharmacokinetic Analysis Set.

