5.5.2 Compliance with study treatment

Compliance with i.v. selexipag treatment is defined as the percentage of the actual dose infused compared with the planned dose to be infused, for each infusion and overall.

The planned dose to be infused will be determined from [Table 6](#) below and based on the subjects' stable Uptravi dose taken from the Visit 2 Day 1 evening dose.

Table 6 Correspondence of i.v. selexipag dose compared to Uptravi oral doses

Uptravi oral dose (μg)	Corresponding i.v. selexipag dose (μg)
200	225
400	450
600	675
800	900
1000	1125
1200	1350
1400	1575
1600	1800

The actual infused dose will be computed by computing the product of the infusion rate (mL/h) with the concentration of infusion solution (μg/mL) as recorded in the eCRF and the elapsed time between start and end time (h) for each infusion to obtain the amount of i.v. selexipag infused.

Missed infusions will be entered with 0 μg actual infusion into the compliance analysis.

The planned dose, actual dose, and resulting compliance will be listed. Compliance will be summarized descriptively for each period and overall.

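### Does the oral-to-i.v. dose factor of 1.125 conflict with the bioavailability data it is said to come from?

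*Protocol*

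**What the plan says.** Protocol Section 5.1.1 gives the aim of the i.v. dosing as an ACT-333679 AUC over the dosing interval comparable to that after oral Uptravi. It names the source: "The correspondence between doses of Uptravi and i.v. selexipag doses were determined based on the results of the absolute bioavailability study (AC-065-110". Table 1 then pairs the eight oral doses from 200 to 1600 µg with i.v. doses from 225 to 1800 µg. SAP Section 5.5.2 reproduces the pairs as Table 6, titled "Correspondence of i.v. selexipag dose compared to Uptravi oral doses".

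Section 1.2.4 of the protocol prints the AC-065-110 geometric mean AUCs from zero to infinity for both analytes and both routes, with 95% confidence intervals. It limits what they cover: "So far a different formulation of i.v. selexipag has been administered to 18 healthy male subjects". The section refers to the Investigator's Brochure. Section 1.4 says that the i.v. dose will target the same exposure to "active metabolite ACT-333679 as with their prescribed dose of Uptravi".

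For analysis, SAP Section 7.8.4.3 estimates the i.v./oral geometric mean ratio of AUC and Cmax with a 90% confidence interval, without a comparability margin. Protocol Section 10.3.1 and SAP Section 8.2 describe the analysis as descriptive, with no confirmatory test.

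**The concern.** A reader who takes Section 5.1.1 literally will divide the Section 1.2.4 metabolite AUCs by dose, expect 1.125 and find 1.27. Nothing in either document explains the difference by a formula, a model, rounding, or an adjustment for formulation, population or steady state.

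The factor sets every subject's planned dose. It also enters the compliance denominator (SAP 5.5.2), the exclusion code in SAP Table 3 for subjects whose i.v. "selexipag dose is not corresponding to" their stable oral dose, and the 200/225 µg normalization (SAP 7.8.3.1). If it were a miscalculation, the exposure premise in the primary objective and in Section 1.4 would rest on a faulty number.

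**Working it through.** **Inputs** (Protocol 1.2.4, geometric mean AUC in h·ng/mL, 95% CI)

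| Route and dose | ACT-333679 | Parent selexipag |
|---|---|---|
| i.v. 200 µg | 14.91 (11.42, 19.47) | 11.16 (9.30, 13.38) |
| oral 400 µg | 37.97 (30.18, 47.78) | 11.04 (8.19, 14.87) |

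**1. The plan's own figures.** Every row of Table 1 gives 1.125, from 225/200 to 1800/1600. The printed AUCs reproduce the metabolite/parent ratios in the same section: 14.91/11.16 = 1.34 and 37.97/11.04 = 3.44. Both sets of numbers are therefore internally consistent, and a misprint is unlikely.

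**2. Crude factor.** Factor = (oral AUC / oral dose) / (i.v. AUC / i.v. dose).

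- Metabolite: (37.97/400) / (14.91/200) = 0.094925 / 0.07455 = 1.273.
- Weighting the parent by the stated 37-fold potency difference gives 1.258.
- Using both lower confidence limits, both upper limits or the interval midpoints gives 1.321, 1.227 and 1.262.

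None of these gives 1.125.

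**3. Face-value prediction at the Table 1 doses.** The i.v./oral metabolite AUC ratio is 1.125/1.273 = 0.88.

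**4. Uncertainty of the crude factor.** Back-calculate the standard errors of the log means from the printed intervals, using t with 17 df (2.110):

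- i.v.: ln(19.47/11.42) / (2 × 2.110) = 0.1264
- oral: ln(47.78/30.18) / (2 × 2.110) = 0.1089

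The standard error of the log ratio is sqrt(0.1264² + 0.1089² − 2ρ × 0.1264 × 0.1089). The within-subject correlation ρ is not reported, so a range is shown.

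| Assumed ρ | 95% interval of the factor | Implied i.v./oral ratio at 1.125 |
|---|---|---|
| 0 | 0.90 to 1.81 | 0.62 to 1.26 |
| 0.5 | 0.99 to 1.64 | 0.69 to 1.13 |
| 0.8 | 1.08 to 1.50 | 0.75 to 1.04 |
| 0.9 | 1.13 to 1.43 | 0.79 to 0.99 |

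The lower limit equals 1.125 at ρ = 0.886. Below that value the tabulated factor lies inside the interval.

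**5. How far either AUC would have to move.** A factor of exactly 1.125 needs an i.v. metabolite AUC of (0.094925/1.125) × 200 = 16.88, or an oral one of 0.07455 × 1.125 × 400 = 33.55. Each lies inside its printed 95% interval.

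**6. Effect on the planned analyses.**

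- *Normalization.* For a subject dosed per Table 1, i.v. dose = 1.125 × oral dose. The i.v. multiplier is then 225/(1.125 × oral dose) = 200/oral dose, which equals the oral multiplier. The normalized ratio is the raw ratio.
- *Compliance and the exclusion code.* Both compare the dose given with the dose tabulated. They measure adherence to the table, whatever its origin.
- *The i.v./oral ratio.* It is estimated from each subject's own Day 1 and Day 3 profiles and borrows nothing from AC-065-110.

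**The case for a change.** The strongest reply is that compatibility with sampling error is not a derivation. The protocol names one study as the basis of the table, that study's point estimate is a different number, and a correlation above 0.89 cannot be ruled out. Section 1.4 leans on matched metabolite exposure. With no margin and no stated expectation, a reader of the final 90% intervals cannot tell an expected departure from 1 from a surprising one. The printed data also put parent exposure at the Table 1 doses at 1.125 × (11.16/200)/(11.04/400) = 2.27 times oral.

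The first part stands: the step from study to table is not written down. The rest does not carry it further. To base a table on a study's results is not to equate its factor with the raw ratio of single-dose geometric means. That formula is the reader's choice, and it carries over a different formulation, healthy men and a 200 µg infusion to patients at steady state on up to 1800 µg. SAP Section 7.8.4.3 reports dose proportionality for oral dosing only; after i.v. dosing, Protocol Section 10.3.5 says AUC proportionality "after selexipag i.v. will be explored by the power model".

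The parent ratio is no evidence about 1.125. Infusion avoids first-pass metabolism, so matching on metabolite raises parent exposure; at a factor of 1.273 the parent ratio would be higher still, 1.273 × 0.0558/0.0276 = 2.57. Writing an expected ratio of 0.88 into the SAP would give benchmark status to an uncertain extrapolation and would alter no estimate, interval or decision.

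**Conclusion.** The two numbers are correctly read, 1.125 in the tables and 1.273 from the printed AUCs, and the documents do not connect them. This is a minor gap in traceability. It does not show that the table or the source statement is wrong, and nothing here bears on which dose is right. A derivation may exist in the Investigator's Brochure or in modelling that the protocol does not reproduce.

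The face-value shortfall in metabolite exposure is about 12% (ratio 0.88). It cannot be called a failure of the aim, because comparable exposure has no limits in the plan and because the interval includes a factor of 1.125 for any ρ up to about 0.89. The interval calculation assumes that the same 18 subjects received both routes (the protocol gives that number only for the i.v. administration), and that kinetics are dose-proportional and time-invariant, so that a single-dose AUC to infinity can stand for the steady-state AUC over a dosing interval.

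No change follows. The missing item is background explanation, the trial estimates the i.v./oral ratio from its own data, and the dependent derivations work the same way whatever the factor's origin.
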